	
 • Hemoglobin ≥ 9 g/dL (or at least ≥ 1 g/dL above baseline) in subjects enrolled with anemia or at least ≥ 1 g/dL above baseline in subjects with symptomatic anemia 
OR
 
 • Platelets $\geq 30 \times 10^9/L$ (or at least $\geq 10 \times 10^9/L$ above baseline) in subjects enrolled with thrombocytopenia 
OR
 
 • Either of the above criteria in subjects with Evans syndrome 
 2. Average weekly requirement of transfused blood component or growth factor requirement (total units of PRBC or Platelets/week, total dose of growth factor/week) by week 12, compared to the week prior to the start of the study drug. 3. Change in corticosteroid dose over time, measured by median daily weight-based prednisone-equivalent corticosteroid dose in a week, from week 1 to week 12 4. Change in other immunosuppressant dose over time, measured by median daily dose of the immunosuppressant in a week, from week 1 to week 12 5. Number of patients who achieved $\geq 50\%$ steroid dose reduction by week 12 compared to week 1 6. Incidence and severity of cGVHD according to 2014 NIH Consensus Criteria, at baseline before the initiation of treatment, and at week 12 
Exploratory endpoints:
 
 1. Absolute percentage change in B cell chimerism pre-treatment, vs weeks 4 and 12. 2. cPRA change in the preformed HLA antibodies before and after treatment in subjects with thrombocytopenia or Evans syndrome 3. Percent MFI change of preformed HLA antibodies before and after treatment. This applies for antibodies with an MFI $>1,000$. 4. Anti-RBC alloantibody titer change in patients with hemolytic anemia before and after treatment 5. Assessment of serial cytokines pre-treatment and weeks 4 and 12. Cytokines include CRP, IL-1, IL-2, IL-6, IFNγ, TNFα, EPO and TPO 6. Immunoglobulin level changes pre-treatment, and weeks 4 and 12. 7. Absolute reticulocyte count, lactate dehydrogenase, haptoglobin changes pre-treatment, and at each biweekly study visit, in patients with anemia or Evans syndrome 8. Change in the weekly rate and severity of bleeding according to the total score of the ITP-Bleeding Scale (IBLS), from week -1 (one week before the start of the study drug) to week 12, in subjects with thrombocytopenia or Evans syndrome

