4 OBJECTIVES AND ENDPOINTS

OBJECTIVES	ENDPOINTS	JUSTIFICATION FOR ENDPOINTS
Primary		
Efficacy of fostamatinib for stable hematologic recovery during post-hematopoietic stem cell transplant immune mediated anemia and/or thrombocytopenia.	
 • The proportion of subjects with hematologic recovery that is stable, defined as improvement documented in 2 consecutive available readings at least 2 weeks apart, without recent blood product transfusion support in the past 7 days. 
Hematologic recovery is defined as:
 
 • Hemoglobin ≥ 10 g/dL (or at least ≥ 2 g/dL above 	The endpoints are all clinically relevant to answer the trial hypothesis and indicative of clinical recovery. The endpoints were chosen to be similar to the previous FIT trials that led to FDA approval of fostamatinib in chronic ITP.

Abbreviated Title: Fostamatinib for post-transplant cytopenias

Version Date: 11/28/2023

	
baseline^{&}) in subjects with posttransplant anemia. In subjects with symptomatic anemia*, a hemoglobin increase of at least ≥ 2 g/dL above baseline is required
 
OR
 
 • Platelets $\geq 50 \times 10^9/L$ (or at least $\geq 20 \times 10^9/L$ above baseline) in subjects with posttransplant thrombocytopenia 
OR
 
 • Both of the above criteria in subjects with posttransplant Evans syndrome 	
Secondary		

Efficacy of fostamatinib for clinically-relevant outcomes in post-hematopoietic stem cell transplant patients
	
1. Proportion of subjects who achieve objective hematologic recovery within the 12-week treatment course defined as:
 
 • Hemoglobin ≥ 9 g/dL (or at least ≥ 1 g/dL above baseline) in subjects enrolled with anemia or at least ≥ 1 g/dL above baseline in subjects with symptomatic anemia 
OR
 
 • Platelets $\geq 30 \times 10^9/L$ (or at least $\geq 10 \times 10^9/L$ above baseline) in subjects enrolled with thrombocytopenia 
OR
 
 • Either of the above criteria in subjects with Evans syndrome 
2. Average weekly requirement of transfused blood component or growth factor requirement (total units of PRBC or Platelets/week, total dose of growth factor/week)
	
The secondary endpoints are all relevant to safety of fostamatinib for post-hematopoietic stem cell transplant setting

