	
by week 12, compared to the week prior to the start of the study drug.
 
 3. Change in corticosteroid dose over time, measured by median daily weight-based prednisone-equivalent corticosteroid dose in a week, from week 1 to week 12 4. Change in other immunosuppressant dose over time, measured by median daily dose of the immunosuppressant in a week, from week 1 to week 12 5. Number of patients who achieved $\geq 50\%$ steroid dose reduction by week 12 compared to week 1 6. Incidence and severity of cGVHD according to 2014 NIH Consensus Criteria, at baseline before the initiation of treatment, and at week 12 	
Tertiary/Exploratory		
The exploratory objective is to evaluate changes in serologic marker while on treatment to identify key biological pathways impacted by fostamatinib that may lead to a response to therapy	
 1. Absolute percentage change in B cell chimerism pre-treatment, vs weeks 4 and 12. 2. cPRA change in the preformed HLA antibodies before and after treatment in subjects with thrombocytopenia or Evans syndrome 3. Percent MFI change of preformed HLA antibodies before and after treatment. This applies for antibodies with an MFI $>1,000$. 4. Anti-RBC alloantibody titer change in patients with hemolytic anemia before and after treatment 5. Assessment of serial cytokines pre-treatment and weeks 4 and 12. Cytokines include CRP, IL-1, IL-2, IL-6, IFNγ, TNFα, EPO and TPO 6. Immunoglobulin level changes pre-treatment, and weeks 4 and 12. 	These exploratory endpoints are relevant to the ex vivo and in vitro analysis that will help predict response and define mechanisms of action of fostamatinib for resolving cytopenias

	
7. Absolute reticulocyte count, lactate dehydrogenase, haptoglobin changes pre-treatment, and at each biweekly study visit, in patients with anemia or Evans syndrome
 
8. Change in the weekly rate and severity of bleeding according to the total score of the IBLS, from week -1 (one week before the start of the study drug) to week 12, in subjects with thrombocytopenia or Evans syndrome[#]
	
--	--	--

&: Baseline is defined as the mean of the last two hemoglobin or platelet measured at least 24 hours apart, at least 72 hours from the last transfusion, within 14 days of the start of the study drug

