5.1 INCLUSION CRITERIA

- Ages 18-75 years inclusive
- Ability to comprehend the investigational nature of the study and provide informed consent
- Female patients of reproductive potential agree to avoid pregnancy through abstinence or the use of two forms of highly effective birth control during and for 1 month after the last study treatment and agree not to donate eggs during this time
- Male patients of reproductive potential agree to avoid pregnancy of a partner through abstinence or the use of two forms of highly effective birth control during and for 1 month after the last study treatment and agree not to donate sperm during this time.
- Diagnosis of an immune mediated cytopenia (anemia and/or thrombocytopenia)[‡] in a patient that either:
 - Failed or relapsed after at least one line of therapy including steroids, IVIG, TPO mimetics, rituximab, azathioprine, cyclophosphamide, cyclosporine, tacrolimus, danazol, vincristine, ESA or splenectomy
 - Or remains transfusion dependent (≥ 1 transfusion(s)/2 weeks)
 - Or is steroid dependent*
- Subjects are ≥ 60 days post-allogeneic transplant with:
 - Thrombocytopenia, defined as average platelets count $< 30 \times 10^9/L$ for 3 consecutive available readings at least 2 weeks apart, after other cell lines have engrafted, with no counts $> 40 \times 10^9/L$ unless from rescue transfusions. Subjects failed at least one line of therapy outlined above with a clinical diagnosis of immune mediated thrombocytopenia.

- Anemia, transfusion dependent, or defined as hemoglobin ≤ 9 g/dL for 3 consecutive available readings at least 2 weeks apart, after other cell lines have engrafted OR if hemoglobin 9-10 g/dL, subject must have symptomatic anemia or ongoing treatment for immune hemolytic anemia that have failed at least one line of therapy outlined above. Symptomatic anemia is defined as anemia with fatigue, weakness, shortness of breath, palpitations/fast heartbeat, lightheadedness, and/or chest pain, and these symptoms are attributed to anemia. Laboratory evaluation are recommended but not required for the diagnosis, such as a positive DAT, low haptoglobin $<$ lower limit of normal (LLN), indirect bilirubin $>$ upper limit of normal (ULN), or lactate dehydrogenase (LDH) $>$ ULN.
- Subjects must test negative for HIV, HBV, and HCV by standard serologic tests within the previous six months

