5.2 EXCLUSION CRITERIA

- Severe psychiatric illness or mental deficiency sufficient to make making informed consent impossible
- Positive pregnancy test for women of childbearing age within 1 week or being actively lactating
- Immune mediated cytopenia responsive to the standard of care treatment
- Immune mediated cytopenia due to other autoimmune causes, such as systemic lupus erythrocytosis, chronic lymphocytic leukemia
- Patients who have previously received or currently take fostamatinib post-allogeneic transplant
- Non-immune mediated cytopenias. Etiologies including, but not limited to, cytopenias due to HIV infection, lymphoproliferative disorders, myelodysplasia/acute leukemia, drug-induced thrombocytopenia, thrombotic microangiopathies, acute bleeding, consumptive coagulopathy, fever, infections leading to cytopenia, medications induced cytopenias, thrombotic microangiopathies (disseminated intravascular coagulation), splenomegaly or hemophagocytic lymphohistiophagocytosis, relapse of primary disease.
- Patients with neutropenia, defined as absolute neutrophil count $\leq 1.0 \times 10^9/L$, will be excluded
- Uncontrolled hypertension (systolic blood pressure ≥ 140 mmHg or diastolic blood pressure ≥ 90 mmHg)

Abbreviated Title: Fostamatinib for post-transplant cytopenias

Version Date: 11/28/2023

- ALT or AST ≥ 3 times the upper limit of normal, or direct bilirubin ≥ 2 times the upper limit of normal
- Patients who have a history of medical disorders, that in the investigator's opinion, could affect the conduct of the study or the absorption, metabolism or excretion of the study drug are excluded.
- Patients with lymphoma/chronic lymphocytic leukemia, hepatitis, or HIV associated with ITP/wAIHA
- Patients with evidence of graft rejection (based on clinical suspicion supported by BM biopsy data and/or chimerism studies and/or MLR)
- Subjects recently treated (within 30 days) with cytokine-targeting biologics (anti-TNF, IL6) or B-cell or plasma-cell depleting antibody.
- Other cancers except that for which the transplant was done < 2 years before study entry, except non-melanoma skin cancer or carcinoma in situ of the uterine cervix or breast

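### Secondary endpoint 1 can be met before the first dose: non-symptomatic subjects may enter at Hb 9-10 g/dL, and Hb of 9 g/dL or more counts as recovery without any rise

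*Combined protocol and SAP*

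**What the plan says.** Secondary endpoint 1 is the "Proportion of subjects who achieve objective hematologic recovery within the 12-week treatment course". For anemia the criterion is "Hemoglobin ≥ 9 g/dL (or at least ≥ 1 g/dL above baseline) in subjects enrolled with anemia", followed by a separate requirement, "or at least ≥ 1 g/dL above baseline in subjects with symptomatic anemia". For subjects with both cytopenias it is "Either of the above criteria in subjects with Evans syndrome". No number of readings, confirmation or transfusion-free interval is stated.

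Section 5.1 opens the anemia criterion with "Anemia, transfusion dependent, or defined as hemoglobin" at or below 9 g/dL on three readings. It then adds a second band: "OR if hemoglobin 9-10 g/dL, subject must have symptomatic anemia or ongoing treatment for immune hemolytic anemia that have failed at least one line". The second half of that condition does not require symptoms.

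Baseline, in the footnote to the section 4 table, is "the mean of the last two hemoglobin or platelet measured at least 24 hours apart, at least 72 hours from the last transfusion", taken within 14 days of the start of study drug. Section 5.2 excludes "Immune mediated cytopenia responsive to the standard of care treatment".

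**The concern.** An endpoint called recovery should not be satisfied by the state in which a subject enters. The plan guards against this in one of the two Hb 9-10 g/dL entry branches, by making symptomatic subjects rise by 1 g/dL. It leaves the other branch open. A non-symptomatic, treated subject who enters at 9.5 g/dL and stays there is reported as recovered.

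The trial has one arm and about 20 evaluable subjects, so the raw proportion is the result for this endpoint. No comparator would show that some successes were present at entry.

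**Working it through.** **The plan's own figures.** The documents give no figure for secondary endpoint 1. The only design figures belong to the primary endpoint (section 9.1: stop if 1 or fewer of 11 respond, reject if more than 4 of 20 respond, rates 10% and 35%). Summing P(X1 = x) × P(X2 ≥ 5 − x) over x = 2 to 11, with X1 ~ Bin(11, p) and X2 ~ Bin(9, p), gives power 0.860 at 35%, as stated, and type I error 0.040 at 10%, within the stated 0.05. Secondary endpoint 1 does not enter this calculation.

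**Step 1: apply the wording to an unchanged subject.** Take a non-symptomatic subject, treated for immune hemolysis after one failed line, with Hb 9.5 g/dL at baseline and throughout.

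| Question | Source | Answer |
|---|---|---|
| May this subject enter? | 5.1, second band | Yes |
| Is a rise compulsory? | 1.1 and 4, symptomatic anemia only | No |
| Is Hb at least 9? | 1.1 and 4 | Yes, from before the first dose |
| Scored as recovered? | 1.1 and 4 | Yes, with a rise of 0 |
| If Evans syndrome, do platelets matter? | 1.1 and 4, either lineage | No |

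The answer does not depend on the number of readings: a steady 9.5 passes whether one, two or six are required. A non-symptomatic subject at exactly 9.0 g/dL, who can enter by the first band, also touches the cut-off.

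**Step 2: weight of one subject.** One automatic success in 20 is 1/20 = 5 percentage points. For example, if the other 19 respond at 10%, the expected proportion is (1 + 19 × 0.10)/20 = 14.5%, against (0 + 19 × 0.10)/20 = 9.5% if this subject is not counted.

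**Step 3: allow for measurement variation.** Some unchanged subjects would also score by chance under a rise rule, so the net effect is below 5 points. Inputs:

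- From the documents: baseline B = mean of two readings (section 4); six on-treatment readings at weeks 2 to 12 (section 1.3).
- Assumed: true Hb uniform on 9-10 g/dL, no drug effect, within-subject SD 0.3, 0.5 or 0.8 g/dL, and any one qualifying reading is enough.

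With 1,000,000 simulated subjects per setting, restricted to measured B of 9-10:

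- As written: P(any reading ≥ 9 or ≥ B + 1)
- Rise required: P(any reading ≥ B + 1)
- Net points per subject = 100 × (difference)/20

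| SD | Correlation between successive readings | As written | Rise required | Net points per subject |
|---|---|---|---|---|
| 0.3 | 0 | 0.999 | 0.014 | 4.9 |
| 0.5 | 0 | 0.999 | 0.19 | 4.0 |
| 0.8 | 0 | 0.998 | 0.50 | 2.5 |
| 0.3 | 0.5 | 0.996 | 0.012 | 4.9 |
| 0.5 | 0.5 | 0.993 | 0.15 | 4.2 |
| 0.8 | 0.5 | 0.985 | 0.40 | 2.9 |

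A hand check at the edge of the band: with true Hb exactly 9.0 and independent readings, P(at least one of six ≥ 9) = 1 − 0.5^6 = 0.984, whatever the SD.

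**Step 4: subjects whose measured baseline falls just under 9.** With independent readings, 8.5%, 14.1% and 21.7% of subjects with true Hb 9-10 have B below 9 (SD 0.3, 0.5, 0.8), and a rule tied to measured baseline does not reach them. Over all subjects with true Hb 9-10, the net effect is 4.5, 3.6 and about 2.4 points per subject.

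**The case against.** The strongest reply is that the affected group is narrow. The subject must be free of symptoms, at Hb 9-10 g/dL, on treatment, and past a failed line. Symptoms are defined broadly in section 4, so fatigue attributed to the anemia already triggers the rise requirement. Section 5.2 removes cytopenias that respond to standard care. The endpoint is handled descriptively (section 9.3.3) and feeds no futility, efficacy or safety rule. All of this stands and limits the importance of the point. It does not close the gap, because section 5.1 expressly admits treated subjects in this band.

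It can also be said that a state present at entry has not been achieved, so a sensible analyst would not score it. That reading is possible, but no rule states it, and two analysts could report different proportions from the same data.

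It is fair to add that a rise rule is imperfect: at SD 0.8 about half of unchanged subjects still score by chance.

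Two stronger readings are tempting. A reader might infer that the primary endpoint's type I error is inflated. The documents do not support this: the primary's absolute cut-off is 10 g/dL, at the top of the entry band, and it needs two consecutive readings at least 2 weeks apart with no transfusion in the preceding 7 days. Any effect of chance crossings would rest on assumed counts and variability, and on which pair of readings counts, since section 9.1 speaks of response at 12 weeks. A reader might also multiply the per-subject figure by several subjects. The documents give no count to multiply by.

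**Conclusion.** The overlap is certain from the text: a subject admitted under section 5.1 can meet secondary endpoint 1 with no change in Hb. Each such subject adds up to 5 percentage points in 20, or 2.5-4.9 points net of chance success under the assumed SD of 0.3-0.8 g/dL and six independent readings. The total effect is unknown and may be zero. The primary endpoint, its type I error and its power are not affected. This should be fixed because the correction is cheap and the proportion has no comparator, but it does not threaten the trial's main conclusion.

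**What to change.** Add to secondary endpoint 1 only, in sections 1.1 and 4:

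*In subjects who are not transfusion dependent at entry, an absolute hemoglobin cut-off already met at baseline (as defined in section 4) does not count as response; the ≥1 g/dL rise above baseline then applies.*

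This is a scoring rule. It uses data already collected and changes no eligibility, visit or treatment. Transfusion-dependent subjects are left out because section 5.1 sets no Hb limit for that route and baseline may be read 72 hours after a transfusion. A further rise from a supported baseline could deny credit to someone who becomes transfusion-free. The sentence therefore leaves their scoring as it is.

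Costs:

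- A few borderline subjects stop counting as responders.
- The required rise steps up at 9 g/dL: a non-symptomatic baseline of 8.9 needs 0.1, while 9.0 needs 1.0.
- Some chance successes remain, and subjects with a measured baseline just under 9 keep the absolute cut-off.
- Section 3.1 uses the same term, objective hematologic recovery, for extended access. It already differs from the endpoint by omitting the symptomatic requirement and by demanding freedom from transfusion support. The difference would widen, so the sections must be reconciled.

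No change to the extended access rule or to the primary endpoint is proposed.

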1 PROTOCOL SUMMARY

1.1 SYNOPSIS

Title:	A Phase II Study of Fostamatinib to Treat Post-transplant Immune-mediated Cytopenias
Study Description:	This open label phase II trial is designed to evaluate the efficacy of fostamatinib in the treatment of post-transplant cytopenias as assessed by hematologic improvement in anemia and/or thrombocytopenia following a 12-week treatment course. Patients who respond to the 12-week treatment course on this single arm study are eligible and have the option to enroll on the extended access trial.
Objectives:	
The primary objective is to assess efficacy of fostamatinib for stable hematologic recovery during post-hematopoietic stem cell transplant immune mediated anemia and/or thrombocytopenia.
 
The secondary objective is to assess efficacy of fostamatinib for clinically-relevant outcomes in post-hematopoietic stem cell transplant patients.
 
The exploratory objective is to evaluate changes in serologic markers that may be associated with cytopenias while on treatment to identify key elements for fostamatinib response.

Endpoints:	
Primary endpoints:
 
The proportion of subjects with hematologic recovery that is stable, defined as improvement documented in 2 consecutive available readings at least 2 weeks apart, without recent blood product transfusion support in the past 7 days.
 
Hematologic recovery is defined as:
 
 • Hemoglobin ≥ 10 g/dL (or at least ≥ 2 g/dL above baseline) in subjects enrolled with posttransplant anemia. In subjects with symptomatic anemia, a hemoglobin increase of at least ≥ 2 g/dL above baseline is required 
OR
 
 • Platelets $\geq 50 \times 10^9/L$ (or at least $\geq 20 \times 10^9/L$ above baseline) in subjects enrolled with posttransplant thrombocytopenia 
OR
 
 • Both of the above criteria in subjects with posttransplant Evans syndrome 
Secondary endpoints:
 
 1. Proportion of subjects who achieve objective hematologic recovery within the 12-week treatment course defined as:

Abbreviated Title: Fostamatinib for post-transplant cytopenias

Version Date: 11/28/2023

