3 STUDY DESIGN

3.1 OVERALL DESIGN

Our plan is to study fostamatinib for the treatment of immune-mediated posttransplant cytopenias (anemia, thrombocytopenia or both)

- This will be a multicenter, open label, phase II study, with no control arm with the primary objective to test the efficacy of fostamatinib in the treatment of posttransplant cytopenias.
- All study participants will receive fostamatinib 100 mg BID for 4 weeks. On the 4-week evaluation, a) if the cytopenia improves (hemoglobin ≥ 10 g/dL, platelets $\geq 50 \times 10^9/L$), patients will continue the same dose for a total of 12 weeks b) if refractory cytopenias persist (hemoglobin < 10 g/dL, platelets $< 50 \times 10^9/L$), subjects will increase dose to 150mg BID. Subjects with persistent (≥ 2 readings, 2 weeks apart) loss of hematologic response after week 5 can increase the study drug dose to 150mg BID until they are at the end of the study on week 12.
- This trial will be done primarily in an outpatient setting. Follow up visits will be completed as outpatient in-person visits at the participating site or via telehealth or telephone if patients are unable to travel for any reason, with labs drawn by local providers in this circumstance.
- The 4-week assessment is the first milestone where dose can be adjusted if necessary. At the end of the trial, participants with objective hematologic recovery will be given the option to enroll onto an extended access trial, including:
 - Post-transplant anemia who achieved a hemoglobin ≥ 9 g/dL (or 1 g/dL above baseline) without transfusion support, at least once in the 12-week phase II study period

Abbreviated Title: Fostamatinib for post-transplant cytopenias

Version Date: 11/28/2023

- Post-transplant thrombocytopenia who achieved a platelet count $\geq 30 \times 10^9/L$ (or $10 \times 10^9/L$ above baseline), without transfusion support, at least once in the 12-week phase II study period
 - Either of the above in subjects with Evans syndrome
- The plan is to treat and include a total of 20 patients in the analysis in this single arm trial.

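### Secondary endpoint 1 can score subjects with no real change as recovered, because its cut-offs overlap the entry criteria and it requires no confirmation or transfusion-free window

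*Combined protocol and SAP*

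**What the plan says.** The first secondary endpoint in Section 1.1, repeated in Section 4, is the "Proportion of subjects who achieve objective hematologic recovery within the 12-week treatment course defined as" either of two routes for each cell line. For platelets it is "Platelets $\geq 30 \times 10^9/L$ (or at least $\geq 10 \times 10^9/L$ above baseline) in subjects enrolled with thrombocytopenia". For anemia it is hemoglobin of at least 9 g/dL or a rise of at least 1 g/dL; symptomatic subjects need the rise. In Evans syndrome either cell line is enough. The definition contains no repeat reading and no transfusion condition.

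Section 5.1 admits subjects with "Thrombocytopenia, defined as average platelets count $< 30 \times 10^9/L$ for 3 consecutive available readings at least 2 weeks apart", and "with no counts $> 40 \times 10^9/L$ unless from rescue transfusions". For anemia it admits transfusion-dependent subjects, those at or below 9 g/dL on three readings, and those at 9-10 g/dL who have symptoms or are on treatment for immune hemolytic anemia after failing a line of therapy.

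Section 4 sets the reference: "Baseline is defined as the mean of the last two hemoglobin or platelet measured at least 24 hours apart", at least 72 hours after a transfusion and within 14 days of starting the drug.

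Section 3.1 uses the same term and cut-offs for roll-over to the extended access trial, and there it says "without transfusion support, at least once in the 12-week phase II study period". The primary endpoint (Sections 1.1, 4 and 9.3.2) uses 50 or +20 for platelets and 10 or +2 for hemoglobin, on two consecutive readings with no transfusion in the past 7 days. Section 9.3.3 analyses the secondary endpoints descriptively.

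**The concern.** The entry rule looks at an average; the endpoint looks at any count during treatment. A subject whose counts vary around the high 20s has a mean below 30 and will, from time to time, give a reading of 30 or more. Before treatment such a reading is compatible with eligibility. After treatment starts, the same reading is a recovery. The absolute route asks for no rise, and nothing in the definition requires the reading to be repeated or to be free of a recent transfusion.

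The hemoglobin arm has a more direct overlap. An asymptomatic subject who enters at 9-10 g/dL under treatment for immune hemolytic anemia already satisfies the absolute cut-off of 9 g/dL.

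This is the first-listed secondary efficacy endpoint of a single-arm trial of 20 subjects. No comparator removes chance recoveries, so a reader of the reported proportion could not tell them from drug responses.

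**Working it through.** **The plan's own figure.** The only design figure belongs to the primary endpoint (Section 9.1): 11 then 9 subjects, stop at 1 or fewer responses, reject at 5 or more of 20. Summing Bin(x; 11, p) × P(Y ≥ 5 − x), with Y ~ Bin(9, p), over x = 2 to 11 gives 0.860 at p = 0.35 and 0.040 at p = 0.10. The stated power of 86% and type 1 error of 0.05 are reproduced. No expected or null rate is stated for secondary endpoint 1.

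**Eligibility against endpoint.** Take entry readings of 25, 35 and 28. The mean is 88/3 = 29.3, below 30, and the maximum of 35 does not exceed 40, so the subject is eligible. If two baseline readings are both 28, baseline is 28. A later count of 30 is a change of 30 − 28 = 2 and scores as recovery.

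**Number of chances.** Section 1.3 schedules a CBC at weeks 2, 4, 6, 8, 10 and 12, which is six readings. If each has probability p of reaching 30 independently, the chance of at least one is 1 − (1 − p)^6: 47% for p = 0.10, 74% for p = 0.20 and 88% for p = 0.30.

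**Simulated false recovery, platelets.** Assumptions, none of them from the documents: log-normal readings around a constant true mean, no drug effect, no transfusion, and within-subject CV of 15-30%. From the documents: the entry filter (mean of 3 below 30, none above 40), baseline as the mean of 2 readings, six on-treatment readings, and recovery at ≥30 or ≥ baseline + 10. True means (× 10^9/L) are spread evenly over the range shown.

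| True means, rule | CV 15% | CV 20% | CV 25% | CV 30% |
|---|---|---|---|---|
| 5-29, one reading | 15% | 22% | 28% | 34% |
| 5-20, one reading | 0.6% | 3.5% | 9.0% | 15.5% |
| 5-15, one reading | 0.04% | 0.8% | 3.3% | 7.4% |
| 5-29, same cut-offs on two consecutive readings | 3.2% | 4.5% | 6.1% | 7.7% |

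At CV 20% the one-reading rate by true mean is 0.2% at 10, 16% at 20, 64% at 25 and 91% at 28. With two consecutive readings, a true mean of 28 still gives about 32-43% over CV 15-30%.

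**Second noise model.** With normal readings at a fixed SD of 2, 3, 5 or 8, the one-reading rate is 65, 83, 92 and 96% at a true mean of 28; 4, 26, 66 and 86% at 25; 0, 2, 26 and 63% at 20; and 0, 2, 22 and 48% at 10. Both models place most of the risk near 30, and both make it depend strongly on the assumed noise.

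**Primary rule.** For platelets, the confirmed rule of ≥50 or +20 gives 0-0.2% for the 5-29 spread in the log-normal model and about 1% or less in the normal model.

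**Hemoglobin.** No simulation is needed for the overlap: an entry range of 9-10 g/dL without symptoms lies at or above the recovery cut-off of 9 g/dL. For symptomatic subjects the +1 g/dL route on one of six readings gives 10, 22 and 33% false recovery at an assumed within-subject SD of 0.4, 0.5 and 0.6 g/dL.

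**The case against.** The looser tier looks deliberate. The primary endpoint is the strict, confirmed one; secondary endpoint 1 sits below it, is descriptive and carries no test. A platelet count of 30 is also an outcome reported for the eltrombopag trial cited in Section 2.1. This stands as a reason to keep the lower cut-offs. It does not justify omitting confirmation or the transfusion condition, and the justification column in Section 4 describes the secondary endpoints only as relevant to safety.

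The size depends on who enrolls. Section 5.1 sets no lower platelet limit and admits transfusion-dependent subjects. If most enter well below 20, the false rate is small. This stands, and it is why three baseline ranges are shown.

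A reader might infer more than the documents support:
- That unchanged subjects are scored as recovered as a rule. At a true mean of 10 and CV 20% the chance is 0.2%.
- That the endpoint itself says one reading is enough. The words "at least once in the 12-week phase II study period" appear only in the extended-access rule, which also requires no transfusion support. For the endpoint, a single reading is an inference from the absence of a confirmation rule.
- That eligible subjects routinely have a baseline of 30 or more. It can happen, but entry readings are 2 weeks apart and baseline readings must fall within 14 days of drug start, so taking two entry readings as baseline is a borderline case.
- That the 28% placebo rate in Section 2.1 is the false rate here. It is about 5 of 18 (exact 95% CI 10-53%), and that trial's entry rule is not given.

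**Conclusion.** The concern holds in a limited form: as written, secondary endpoint 1 can score a subject with no real change as recovered. Two causes can be read directly from the text. The absolute cut-offs overlap the entry criteria in both cell lines, and the definition lacks the confirmation and transfusion-free conditions that the primary endpoint has.

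The size is uncertain because the documents supply neither within-subject variability nor a baseline distribution. Across the assumptions used, the platelet false recovery rate runs from near 0% to about 34%, with the risk concentrated in subjects entering in the 20s. It would be wrong to conclude that the trial's main result is inflated: the primary endpoint, the two-stage decision and the sample size do not use this definition. The consequence is a secondary proportion that may be too high and is hard to interpret without a control arm.

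**What to change.** In Sections 1.1 and 4, change secondary endpoint 1 as follows:

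1. Apply the primary endpoint's rule: two consecutive readings at least 2 weeks apart, with no transfusion in the past 7 days.
2. Let the absolute routes (platelets ≥30 × 10^9/L, hemoglobin ≥9 g/dL) count only for subjects whose baseline is below that cut-off. All others need the rise already stated (+10 × 10^9/L or +1 g/dL).
3. Report the absolute and rise-from-baseline routes separately.

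Step 2 keeps the absolute route meaningful; demanding a +10 rise from everyone would make it redundant. Step 3 is needed because steps 1 and 2 do not remove the problem near the line: an unchanged subject with a baseline of 28 can still give two readings of 30 or more by chance.

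The extended-access eligibility rule in Section 3.1 can stay as it is, but under a different name, so that one term does not carry two definitions.

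The cost is wording only, with no new visits or data. The secondary response rate will be lower, and a subject whose first recovery is at week 12 will not be counted.
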